Commercially available DBS leads in the US consist of a linear array of ring-shaped electrodes. We are studying segmented leads developed by Boston Scientific to steer current and better optimize DBS efficacy and tolerability in individuals. Evidence from recent studies in Europe by Timmermann et al and Volkmann et al suggest that this current steering approach is feasible for these purposes, however it is possible that the activation of individual segments alone will not provide therapeutic benefit or that they will not improve the thresholds for potential side effects from DBS in individual patients. If this were the case, we can still activate all three segments simultaneously so that the individual segments act together as a traditional ring electrode.

15. Participants (Screening and Selection)

a. How many participants are to be enrolled at UAB? 40

If multi-center study, total number at all centers:

Not applicable, this is a single center study

b. Describe the characteristics of anticipated or planned participants.

Sex: Both

Race/Ethnicity: All

Age: 18 - 70

Health status:

Patients who undergo deep brain stimulation (DBS) as part of routine care for Parkinson's Disease

Note. If data from prior studies indicate differences between the genders or among racial/ethnic groups in the proposed research or if there are no data to support or to negate such differences, Phase 3 clinical trials will be required to include sufficient and appropriate entry of gender and racial/ethnic subgroups so that trends detected in the affected subgroups can be analyzed. If ethnic, racial, and gender estimates are not included in the protocol, a clear rationale must be provided for exclusion of this information. If prior evidence indicates that the results will not show gender or racial differences, researchers are not required to use gender or race/ethnicity as selection criteria for study participants. They are, however, encouraged to include these groups. See Section II. Policy of the NIH POLICY AND GUIDELINES ON THE INCLUSION OF WOMEN AND MINORITIES AS SUBJECTS IN CLINICAL RESEARCH – Amended, October, 2001) for further details.

c. From what population(s) will the participants be derived?

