Intraoperative ERP assay: DBS surgery occurring electively as part of routine care. We only consent patients after the patient has been approved for surgery for routine care. Our research approach in the OR uses a unique electrophysiological assay to measure cortical activation by DBS with high bandwidth simultaneous EEG, ECOG (over pre-motor, primary motor, and primary sensory cortices), and 8 contralateral surface EMG electrodes. We measure cortical activation by DBS in a dose-dependent manner, elicited from the entire spatial extent of the implanted lead. EEG, ECOG, and EMG are validated modalities that have been in worldwide clinical use for decades. As such, putative biomarkers from this study have the potential for broad, immediate application. Our unique electrophysiology approach allows (1) remarkable stimulus artifact removal; (2) accurate detection of small differences in ERP latency; (3) explicit control of the timing, waveform, and pattern of the stimuli, (4) fully automated stimulus protocol delivery, and (5) markedly faster post-processing. This allows us to evaluate hypotheses that were untestable in prior DBS studies. We use our externalized pulse generator to randomize stimulus amplitude (0 to 5 mA in 1 mA increments), location (anode/cathode pair), and interstimulus interval (mean 100±20 ms) on a pulse by pulse basis. We will elicit ERPs only from adjacent electrode pairs, yielding 25 stimulation conditions. Based on extensive prior work, 100 stimulation events (50 in each anode/cathode pair) is more than sufficient to generate an ERP in the vast majority of participants. The total duration of the assay is 24.0 minutes.

Neuroimaging Battery: All imaging studies including MRI and CT occur as part of routine care. Data from the imaging studies will be used for research purposes. Imaging will occur (1) pre-operatively for screening and diagnostic purposes, (2) to inform routine stereotaxy on the day of surgery, (3) to localize ECOG, EEG, and DBS electrodes during surgery, and (4) to confirm lead placement and screen for potential adverse events after surgery.

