9. External delivery of electrical pulses through the DBS wire with the MultiChannel STG 4000 stimulator: Prior to any use of the STG4000 in human subjects, we connected it to an externalized Medtronic DBS lead in the lab. This lead was connected to a resistor approximating the resistance of the human brain tissue (2 kOhms), and an oscilloscope verified the amplitude and timing of the stimulus pulse when compared to that of the commercial device. Potential risks of using the STG4000 in this protocol are minimal for the following reasons:
 - a. This is a research protocol. The results of the ERP assay do not alter surgical care or decision-making, and the STG4000 is only used temporarily.
 - b. The proposed studies only deliver single pulses with narrow pulse widths (~60 to 120 microseconds), and we do not deliver chronic, continuous stimulation at greater than 100 pulses per second over a period of years or even decades (as occurs with routine clinical care).
 - c. Stimulus intensity will always be well within the established safety limits for electrical stimulation of neuronal tissue mandated by the FDA (less than 30 μ coulombs/cm²/phase, a conservative estimate of the amount of charge delivery that could cause irreversible damage to human nervous tissues).
 - d. We always verify normal tissue impedance with the impedance testing function prior to any experimental stimulation. Additionally we use the therapeutic impedance measurement to convert the stimulation voltage to its corresponding constant current value with the external stimulator. This ensures that the current delivered during this experiment is never greater than the FDA-mandated limit from item 4.c. above.
 - e. Each stimulus pulse is charge-balanced, such that there is no net delivery of charge into the brain.
 - f. Our stimulus isolation units are optically isolated and powered by detachable batteries, such that there is no electrical connection between the wall outlet and the neural tissue of the participant. There is no risk for a power surge from the electrical outlet entering the brain of a participant.
 - g. The PI stimulated himself with an externalized DBS electrode connected to both the commercial DBS and the STG4000 stimulator to verify that identical threshold stimulation parameters elicited tingling of the skin.
 - h. This external stimulator system has been used on numerous patients in other protocols without subjective or objective adverse consequences.

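### Protocol item 19.a.9.d claims that a current check keeps stimulation under a charge-density limit, but current alone cannot show that

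*Protocol*

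**What the plan says.** The relevant text is in Protocol item 19.a.9, on delivering research pulses through the implanted lead with the external stimulator.

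- **Item 9.c** sets the limit: "Stimulus intensity will always be well within the established safety limits for electrical stimulation of neuronal tissue mandated by the FDA". It expresses that limit as less than 30 µC/cm² per phase.
- **Item 9.d** names the mechanism. After an impedance test, "we use the therapeutic impedance measurement to convert the stimulation voltage to its corresponding constant current value with the external stimulator". It then concludes: "This ensures that the current delivered during this experiment is never greater than the FDA-mandated limit from item 4.c. above". Item 4 has no sub-item c, so 9.c must be meant.
- **Item 9.b** gives the pulses as "single pulses with narrow pulse widths (~60 to 120 microseconds").
- **Item 16.a (Intraoperative ERP assay)** gives the amplitude: "We use our externalized pulse generator to randomize stimulus amplitude (0 to 5 mA in 1 mA increments"). Pulses go only through adjacent contact pairs, and pulse width is not listed among the randomized parameters.
- **Item 18.a.9** says that the experimental pulses pass through the segmented contacts.
- **The opening of item 19.a.9** describes a bench test of the stimulator: "we connected it to an externalized Medtronic DBS lead in the lab", and "an oscilloscope verified the amplitude and timing of the stimulus pulse when compared to that of the commercial device".

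No contact area, worked charge density, or amplitude cap derived from the limit appears in either document.

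**The concern.** The limit and the check are in different units. The limit is charge per unit area per phase; the check yields a current. The same current can fall on either side of the limit, depending on how long the pulse lasts and how much metal it passes through.

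Area is also the quantity that this trial's lead changes. Items 14 and 19.a.4 say that one can "activate all three segments simultaneously so that the individual segments act together as a traditional ring electrode". A single segment is therefore smaller than the ring, while the current reading in 9.d would be identical for both.

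Item 9.d is the only part of item 9 that names a mechanism for keeping this limit, and it covers research-only stimulation during awake surgery. Someone relying on it could not tell a contact pair that meets the limit from one that does not.

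**Working it through.** **Inputs from the protocol**

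- Maximum amplitude: 5 mA (item 16.a)
- Pulse width: about 60 to 120 µs (item 19.a.9.b); the width used at 5 mA is not stated
- Limit: less than 30 µC/cm² per phase (item 19.a.9.c)
- Contact area: not stated, so it is varied below as an assumption

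The plan states no delivered charge density, so there is no figure of its own to reproduce.

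**Step 1. Charge per phase.** Q (µC) = I (mA) × pulse width (µs) ÷ 1000.

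- 5 × 60 ÷ 1000 = 0.30 µC
- 5 × 90 ÷ 1000 = 0.45 µC
- 5 × 120 ÷ 1000 = 0.60 µC

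**Step 2. Area at which the limit is reached.** A = Q ÷ 30.

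- 60 µs: 0.30 ÷ 30 = 0.010 cm² = 1.0 mm²
- 90 µs: 0.45 ÷ 30 = 0.015 cm² = 1.5 mm²
- 120 µs: 0.60 ÷ 30 = 0.020 cm² = 2.0 mm²

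Both contacts of an anode/cathode pair carry the same charge, so the smaller one sets the density and must exceed these values.

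**Step 3. Density at 5 mA over assumed areas.** Density = Q ÷ A, in µC/cm² per phase.

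| Assumed area | 60 µs | 90 µs | 120 µs |
|---|---|---|---|
| 1.0 mm² | 30 | 45 | 60 |
| 1.5 mm² | 20 | 30 | 40 |
| 2.0 mm² | 15 | 22.5 | 30 |
| 3.0 mm² | 10 | 15 | 20 |
| 6.0 mm² | 5 | 7.5 | 10 |

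The current is 5 mA in every cell, yet the density runs from 5 to 60 and crosses the limit of 30.

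**Step 4. Segment versus ring.** Assume that three equal segments make up a ring and share current equally. One segment alone then has three times the ring's density at the same current and pulse width. For a single segment to comply at 5 mA, the combined area of the three must exceed 3 × 1.0 = 3.0 mm² at 60 µs, and 3 × 2.0 = 6.0 mm² at 120 µs. With the current spread over the ring, 1.0 to 2.0 mm² combined would be the threshold.

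**Step 5. Do the other safeguards in item 19.a.9 supply the missing step?**

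- The bench test used a different manufacturer's lead and a resistor, and checked pulse amplitude and timing. It says nothing about density at the trial lead's contacts.
- Charge balance (9.e) concerns net charge, not density within a phase.
- Earlier use of the stimulator (9.h) is cited without naming the lead.
- Cautious stepping from low to high intensity (9.j) describes routine care, whereas the assay randomizes amplitude from pulse to pulse.

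**The case against.** The strongest reply is that item 9.d should not be read alone. Item 9.c, directly above it, commits the study to the limit in the correct units. Items 9.b and 16.a together bound the charge at about 0.60 µC per phase. For a given contact and pulse width, density is proportional to current, so controlling delivered current is a sensible part of keeping to the limit. What is wholly missing is one fixed constant, the contact area. It may well be in the device review sheets that item 8 says are attached, and Milestone 1.2 requires FDA approval of the directional system before the study starts. Every density above comes from an assumed area, and the bench test was never offered as proof of charge density.

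Much of this stands. The commitment in 9.c remains, the sheets may hold the area or the whole calculation, and the table shows a range of possibilities rather than evidence of a breach. But 9.c asserts the outcome without showing how it is reached, and 9.d, which does offer a mechanism, neither uses the area nor cites a document that gives it. Controlling current becomes a control on density only after someone has worked out which current is allowed for each contact, and that step does not appear.

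**Conclusion.** The concern holds. Item 9.d attributes to its check a property that the check does not have. At the stated maxima, compliance depends on whether the smaller active contact exceeds 1.0 mm² (60 µs) to 2.0 mm² (120 µs), and nothing in 9.d bears on that.

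This is not a finding that the limit is exceeded. If the smaller contact is above 2.0 mm², every stated setting complies and one sentence would show it. If it is smaller, whether a cap is needed depends on the pulse width used. The thresholds in mm² follow from the protocol's own figures. The densities in the table rest on assumed areas, and the factor of three rests on equal segments sharing current equally. The point should be corrected because it concerns a stated safety assurance and is cheap to settle.

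**What to change.** Replace the guarantee in 9.d with a calculation completed before the first case. For each adjacent pair, take maximum amplitude × the pulse width actually used ÷ the area of the smaller contact on the trial lead, and compare the result with 30 µC/cm² per phase. If a device review sheet already contains this calculation, cite it in 9.d.

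For any pair that does not comply, cap amplitude or pulse width. For example, an assumed 1.5 mm² contact (0.015 cm²) allows less than 30 × 0.015 = 0.45 µC per phase. That means staying below 0.45 µC ÷ 5 mA = 90 µs at full amplitude, or below 0.45 µC ÷ 120 µs = 3.75 mA at the widest pulse.

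Keep the impedance test, described as a check that the contact is working. Correct the cross-reference from 4.c to 9.c.

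The cost is one calculation from the manufacturer's contact area, or one citation, and a short rewording. The downside is that a cap, if needed, would remove some of the assay's stimulation conditions on the affected contacts.

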Our routine practice is to place unilateral DBS in the most affected side of the brain, followed by contralateral surgery, if and when it is indicated based upon motor symptoms. PD motor symptoms are typically asymmetric with respect to the side of the body that is affected most, and this asymmetry persists lifelong within an individual. The per protocol analysis for our project evaluates unilateral and not bilateral DBS over the first 6 months of therapy, followed by an open label evaluation at a Study Exit visit at 1 year after surgery. We have budgeted the necessary number of devices for contralateral surgery in a subset of participants over the entire 5-year duration of the study, based upon our prior publications in this area³⁵⁻³⁶ and a review of a large consecutive series from our clinical practice (please see blue trace on the figure above). Based upon these data, we anticipate potentially needing to place contralateral DBS within 6 months of unilateral surgery for the BRAIN Initiative study in <10% of participants. This is likely an overestimate, because we are recruiting participants who understand that we want to avoid the second surgery within the first year if possible and who are on average at an earlier disease stage versus most prior DBS studies.

Similar to other commercially available devices, the Boston Scientific Vercise PC battery has not been, nor will it ever be, declared safe for brain or body MRI. If participants require contralateral DBS for the other side of their brain, lack of MRI on the day of their second surgery could make targeting of the implanted electrode less optimal in some cases if we use CT images for targeting. Risk is mitigated because we can use intraoperative imaging to mirror the location of their other DBS lead to target the opposite side of the brain. Additionally, as part of routine care we have implanted a number of DBS electrodes with CT targeting in patients who have MRI contraindication for other reasons (cardiac pacemakers, spinal cord stimulators, shrapnel in the body from accidents) with good clinical outcomes.

Symptoms related to participants being "off" their dopaminergic medications can be easily alleviated by having them take a dose of their medications. Participants will be instructed to bring their medications with them to the off medication assessments and will be allowed to take them immediately following testing.

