Rationale:	Overall randomization and study design has been approved by NIH staff. As this is a deviation from what was originally in the proposal, this new study design should be followed. All further deviations should be negotiated and approved by NIH prior to changes being made.
Milestone 1.6:	Form Scientific Steering Group and hold a meeting to review project status, problems and direction.
Success Criteria:	Meeting participants, proceedings and decision(s) will be communicated to NIH program staff.
Rationale:	This is a requirement of the RFA and will help to ensure continued progress and success of the project.
Milestone 1.7:	Review IRB and IDE paperwork to ensure both are up to date and allow for a sufficient scope and number of subjects for successful completion of work proposed in the upcoming year.
Success Criteria:	Confirm paperwork is up to date and NINDS staff has the most recent version.
Rationale:	Maintaining IRB and IDE approval is a requirement for a clinical study.

Year 2

Milestone 2.1:	Maintain active membership status in NIH-coordinated data sharing consortium.
Success Criteria:	Actively participate in the data sharing consortium, and adopt best practices/efforts and comply with the recommendations of the data sharing consortium, throughout all years and/or stages of the award.
Rationale:	Participation and maintaining an active membership status in the consortium is a requirement of the RFA.
Milestone 2.2:	Complete the pre-operative assessment battery and implant the Boston Scientific Vercise DBS system with the directional lead in at least 12 participants by the end of Y2.
Success Criteria:	Successfully implant the Vercise DBS system with directional lead, extension cable, and pulse generator in 12 participants using standard STN stereotaxy. Successful implant is defined as placement of the entire DBS system without surgical adverse events (such as stroke, infection, seizure) or any other adverse event that prevents postoperative device activation, adjustment, and/or behavioral testing. Results will be recorded in a surgical implantation document form including system tests showing normal DBS electrode impedances and typical behavioral responses during test stimulation in surgery (i.e., side effect and efficacy thresholds). These data will be summarized at the time the yearly annual report for Y2 is submitted.

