Rationale:	Our goal to implant 12 (or more) participants by the end of Y2 will enable initial follow-up and randomization in these participants during Y2 and Y3. Based on our clinical volume and experience in past studies, we can typically recruit 1 to 3 patients per month who are undergoing STN DBS for PD.
Milestone 2.3:	Acquire and analyze intraoperative cortical physiology during surgery in the initial 12 participants from Milestone 2.2.
Success Criteria:	Demonstrate delivery of the experimental stimuli through the directional lead during surgery, removal of the stimulus artifact ($\geq 85\%$ amplitude reduction) in EEG and ECoG channels in $\geq 80\%$ or 10/12 of participants, and measurement of event related potential (ERP) waveforms (with latency and amplitude measurements from both P1/N1 and HFO responses in $\geq 75\%$ or 9/12 of participants), as shown in our prior publications and pilot data (proposal Figs. 2-5). These data will show feasibility for SA 1.2. We will co-register intraoperative O-arm CT images with pre-op brain MRI to localize ECoG, EEG, and DBS contacts.
Rationale:	In this first-in-human approach, we will measure patient-specific cortical activation patterns elicited by directional DBS with simultaneous EEG/ECoG. Our goal is to use these methods to optimize and expedite field shaping with novel directional DBS lead technology.
Milestone 2.4:	Determine whether current steering alters the therapeutic window within individual participants during initial device activation in the Monopolar Survey (SA 1.1).
Success Criteria:	Demonstrate $\geq 20\%$ increase in therapeutic window in at least one electrode contact segment versus conventional omnidirectional DBS ("ring mode") in $\geq 40\%$ of the participants who have completed the monopolar survey by the end of Y2. Additionally, we will classify all stimulation side effects by type (i.e., motor, sensory, oculomotor, ataxia, autonomic, etc.). To maintain blinding, patients will not be told which survey is being performed or which treatment condition they will receive.

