Rationale: In this first-in-human approach, we will reversibly activate unique combinations of DBS contact segments, guided by cortical physiology and behavioral criteria, to explore putative biomarkers to guide field shaping with multiple directional DBS contacts. This dose-finding and safety study will directly inform contact selection for the final arm of the double-blind crossover and other related milestones.

Behavioral criteria for contact selection in SA2.1 arise from the Monopolar Survey and will be defined as the 3 lead segments with the lowest floor of the therapeutic window. As previously, if we were unable to demonstrate changes in therapeutic window floor with directional DBS either at the individual or group level in Milestone 2.4, we would instead use the three contacts that displayed the greatest therapeutic window magnitude or percent improvement in UPDRS hemibody subscore for the stimulated side of the body. Behavioral criteria for contact selection in SA2.2 will be defined as the 3 lead segments with the lowest (worst) stimulus amplitude thresholds for adverse capsular motor side effects (involuntary contraction of the mouth, arm, or leg).

Cortical physiology criteria for contact selection in SA2.1 arise from analyses of intraoperative EEG/ECoG studies in Milestone 2.3. We have previously demonstrated that within-participant changes in P1/N1 amplitude are associated with the magnitude of improvement in motor symptoms during high frequency DBS for PD and essential tremor. Thus, EEG criteria for contact selection in SA2.1 are peak latency of ≥ 550 μ sec (proposal **Fig. 3D**) and absence of the large amplitude HFO (proposal **Fig. 4C**). We will rank and simultaneously activate the 3 most promising lead segments that meet the above criteria based upon P1/N1 peak amplitude. The EEG criteria for SA2.2 are P1/N1 latency < 550 μ sec (proposal **Fig. 3D**) and presence of the HFO (proposal **Fig. 4C**). We will then rank and simultaneously activate the 3 lead segments based upon P1/N1 peak amplitude. In addition to these criteria, we will also investigate whether directional stimulation alters the spatial distribution of ERP responses on the ECoG strip.

Milestone 2.7: **Establish cognitive and behavioral safety related to directional versus omnidirectional DBS.**

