Success Criteria: No more than 2 patients experience worsening on more than 30% of the test scores as quantified as more than a 1.5 standard deviation score decline beyond any identified level of change, as reported from the DBS surgery literature.

Rationale: Although conventional bilateral STN DBS is safe cognitively and behaviorally at the group level, an important goal is to identify potential changes related to the field shaping approach; we are positioned to sensitively detect these changes within subjects, should they occur. If risks are identified that are beyond those reported in the literature, conventional DBS in ring mode is still available.

Milestone 2.8: **Safety Monitoring Committee will meet to discuss all AEs and SAEs at the end of Y2.** This committee will also meet on an as-needed basis following SAEs to determine whether they are study-related versus a known complication of DBS surgery.

Success Criteria: Meeting proceedings and decisions will be communicated to the PI and NINDS program officers.

Rationale: This process will ensure ongoing safety of the study

Milestone 2.9: **Participant enrollment follows approved protocol.**

Success Criteria: All subjects follow research protocol as summarized in **Error! Reference source not found.** and **Error! Reference source not found.** Follow-up at 1 year post-crossover completion with ≥80% of the participants.

Rationale: Overall randomization and study design has been approved by NIH staff. As this is a deviation from what was originally in the proposal, this new study design should be followed. All further deviations should be negotiated and approved by NIH prior to changes being made.

Milestone 2.10: **Hold a Scientific Steering Group meeting to review project status, problems and direction.**

Success Criteria: Meeting participants, proceedings and decision(s) will be communicated to NIH program staff.

Rationale: This is a requirement of the RFA and will help to ensure continued progress and success of the project.

Milestone 2.11: **Review IRB and IDE paperwork to ensure both are up to date and allow for a sufficient scope and number of subjects for successful completion of work proposed in the upcoming year.**

Success Criteria: Confirm paperwork is up to date and NINDS staff has the most recent version.

Rationale: Maintaining IRB and IDE approval is a requirement for a clinical study.

Year 3

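### Milestone 2.7 is headed as directional versus omnidirectional cognitive safety, but its criterion does not contrast the two conditions and caps events at 2 patients with no denominator

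*Protocol*

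**What the plan says.** Protocol item 23, Milestone 2.7, is headed "Establish cognitive and behavioral safety related to directional versus omnidirectional DBS". Its success criterion is "No more than 2 patients experience worsening on more than 30% of the test scores", with worsening of a score defined as "more than a 1.5 standard deviation score decline beyond any identified level of change, as reported from the DBS surgery literature". No number of patients is given for the limit of 2 to refer to. The criterion does not name the stimulation condition or visit that counts, the literature values, or the source of the SD. The rationale adds that "we are positioned to sensitively detect these changes within subjects, should they occur", but no decision rule follows from that.

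Four other places bear on this:

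- **Number available.** Milestone 2.2 plans implants "with the directional lead in at least 12 participants by the end of Y2", and its rationale says this "will enable initial follow-up and randomization in these participants during Y2 and Y3".
- **Data collected.** The procedures table in item 16.e schedules the cognitive/behavioral battery pre-op and at crossover visits 4b, 5b and 6b, so there is a score after each condition.
- **Neighbouring milestones.** 2.4 and 2.6 both set success as at least 40% of those who reached the relevant survey, and both measure change against omnidirectional DBS.
- **SAP.** Under SA2, the crossover (SA2.3) is to compare cognitive and behavioral function, among other outcomes, across the programming strategies. Within-participant cognitive/behavioral change is listed as a secondary measure. Neither the 1.5 SD and 30% definition nor Milestone 2.7 is mentioned.

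**The concern.** The heading promises a comparison between two ways of stimulating, and the rule delivers a count against an outside reference. If the milestone is reported as met, a reader will take it that directional stimulation was shown to be no worse for cognition than ring-mode stimulation in these patients. The rule can be satisfied without anyone looking at that contrast.

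A limit of 2 also has no fixed meaning until the number tested is known. The same two patients are a modest fraction of a full Year 2 cohort and a third of a half-sized one. This is the only numeric cognitive safety criterion among the milestones; Years 3 to 5 contain no equivalent.

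**Working it through.** There is no stated calculation to reproduce: the documents give no sample size, tolerable rate or error rate for the limit of 2.

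**1. Does the rule measure the contrast?** For one test score in one patient, let D_dir and D_omni be the decline from the reference assessment under each condition, in SD units, and let L be the literature change. The criterion does not name the reference; item 16.a describes the battery as measured against pre-op baseline.

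- The milestone rule, applied in a directional period, counts the score if D_dir > 1.5 + L.
- A directional versus omnidirectional rule counts it if D_dir − D_omni > 1.5, that is, if D_dir > 1.5 + D_omni.

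The two agree for every D_dir only when D_omni = L, that is, when the patient's own omnidirectional change equals the literature change. If D_omni < L, any D_dir between 1.5 + D_omni and 1.5 + L is a marked directional excess that the milestone does not count. If D_omni > L, the milestone can count decline that is not specific to directional stimulation. So the count does not stand in for the contrast.

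**2. How many patients could be tested by the end of Year 2?** Item 16.a puts activation about 1 month after surgery and each condition at 2 months. The first post-operative cognitive visit (4b) therefore falls about 1 + 2 = 3 months after implant, and the second (5b) about 1 + 2 + 2 = 5 months after. Patients implanted late in Year 2 cannot contribute by year end. The target of 12 is a minimum for implants, not a count of patients tested. I use n = 12 (all of the minimum target tested) and n = 6 (half of it, my illustration).

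**3. What two events mean** (exact Clopper-Pearson 95% intervals):

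- 2/12 = 16.7%, interval 2% to 48%.
- 2/6 = 33.3%, interval 4% to 78%.

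**4. How often the rule passes.** P(pass) = P(X ≤ 2) for X binomial(n, p). At an assumed p = 20%:

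- n = 12: 0.8^12 + 12(0.2)(0.8^11) + 66(0.2^2)(0.8^10) = 0.069 + 0.206 + 0.283 = 0.558.
- n = 6: 0.8^6 + 6(0.2)(0.8^5) + 15(0.2^2)(0.8^4) = 0.262 + 0.393 + 0.246 = 0.901.

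The documents give no rate of marked decline, so a range is needed:

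| Assumed rate | P(pass), n = 6 | P(pass), n = 12 |
|---|---|---|
| 5% | 0.998 | 0.980 |
| 10% | 0.984 | 0.889 |
| 15% | 0.953 | 0.736 |
| 20% | 0.901 | 0.558 |
| 25% | 0.831 | 0.391 |
| 30% | 0.744 | 0.253 |

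The dependence on n is slight at 5% and large from 15% upward, which is where a safety rule needs to discriminate.

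**The case against.** The best defence is that this is a Year 2 progress milestone, not a trial endpoint. It does not recur in later years, the SAP does not rely on it, and a safety committee reviews adverse events yearly and as needed. Screening for decline beyond what is expected after DBS surgery is coherent in itself, and the rationale notes that ring mode remains available if excess risk appears. Milestone 2.3 states its criteria out of 12, so 2 of about 12 may have been meant. All of this is fair. It is a reason to keep the screen and to treat this as a wording correction. It does not make the criterion match its heading, and the denominator of 12 is a guess that the text does not confirm.

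Three stronger readings are tempting, and the documents do not support them:

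- **That the trial would never compare the two conditions on cognition.** The SAP plans that comparison under SA2.3, with conventional DBS as one of the strategies. What is missing is the link to the milestone. A comparison of mean scores also need not reveal marked decline in a few patients.
- **That the rule should be judged at 30 patients.** That is the Year 4 implant total; this milestone falls in Year 2.
- **That the literature allowance is a bilateral one, wrongly applied to a study that** "evaluates unilateral and not bilateral DBS over the first 6 months of therapy". The criterion cites the DBS surgery literature in general. Bilateral stimulation appears only as background in the rationale ("Although conventional bilateral STN DBS is safe cognitively and behaviorally at the group level"), so the link is an inference. Whether the allowance would hide real decline depends on published values that the documents do not give.

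**Conclusion.** The point stands, limited to the milestone. Milestone 2.7 can be declared met without the directional versus omnidirectional comparison in its heading, and its limit of 2 has no stated denominator. Two events could mean 17% of patients with an upper limit of 48%, or 33% with an upper limit of 78%. At an assumed 20% rate of marked decline, the chance of passing is 56% at 12 tested and 90% at 6.

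The mismatch between heading and criterion rests on the text alone and needs no assumption. The sizes rest on an assumed decline rate, on independent patients, and on 6 and 12 as illustrative numbers tested. They show how far the rule's strictness depends on an unstated number; they do not predict the result.

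**What to change.** 1. **Keep the existing count as a safety screen.** State that it is against pre-op scores and the literature change, and give the literature values and the SD used. Report it with the number of patients tested and an exact 95% CI.
2. **Add the paired result.** Using the same definition (more than 1.5 SD, on more than 30% of tests), report the proportion of patients whose directional-condition scores are worse than their own omnidirectional-condition scores, among those who completed both conditions, with an exact 95% CI.
3. **Report the behavior-guided and ERP-guided conditions separately.** Item 16.a describes random allocation to three conditions, but Table 3 places the EEG/ECoG-guided condition after the two randomized ones. For any condition not given in randomized order, note that order and practice effects may contribute to the difference.
4. **Base any directional versus omnidirectional safety statement on the paired result**, and cross-refer to SA2.3 in the SAP.

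The cost is milestone wording and one table. No new visits or tests are needed, because the battery is already given at 4b, 5b and 6b. The drawback is that few patients will have completed both conditions by the end of Year 2, so the paired interval will be wide then.
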